#### **17.1.1.1 Severity**

Severity is classed as mild, moderate, severe. AEs starting after the first dose of Fabrazyme/AGA BETA BS with a missing intensity will be classified as severe. If a patient reports a TEAE more than once within that SOC/PT, the AE with the greatest intensity will be used in the corresponding intensity summaries.

#### **17.1.1.2 Relationship to Study Medication**

Relationship, as indicated by the investigator, is classed as “Related”, “Not related”.

AEs starting after the first dose of Fabrazyme/AGA BETA BS with a missing relationship will be classified as “Related”. If a patient reports the same AE more than once within that SOC/PT, the AE with the worst-case relationship to study medication (AGA BETA BS) will be used in the corresponding summaries.

#### **17.1.2 AEs Leading to Discontinuation of Study Medication**

AEs leading to permanent discontinuation of patient will be identified by using Action taken as Discontinued in the CRF under Adverse Event.

AEs leading to discontinuation of patients from treatment will be listed with the reasons for discontinuation.

#### **17.1.3 Serious Adverse Events**

Serious adverse events (SAEs) are those events recorded as “Serious” on the Adverse Events page of the (e)CRF.

A summary of serious AEs by SOC and PT will be prepared.

Serious adverse event (SAEs) leading to patient discontinuation will be summarized.

See [appendix 1](#) for handling of partial dates for AEs. In the case where it is not possible to define an AE as treatment emergent or not, the AE will be classified by the worst case; i.e. treatment emergent.

SAE will be listed, and summary will be provided for treatment period.

#### **17.1.4 Adverse Events Leading to Death**

Adverse Events Leading to death will be presented as a listing for ITT population.

---

Document: \\needc-vnasc01\Biosdata\Biosidus\Agalsidase Beta\YZAA1358\Biostatistics\Documentation\SAP

Author: [name]

Version Number: V1.0

Version Date: 08May2025

Template No.: CS\_TP\_BS016 Revision 7

Reference: CS\_WI\_BS005

Effective Date: 01Nov2021

### 17.1.5 Infusion Associated reaction(IAR)

An AE related to the infusion of study drug is referred to as an Infusion associated reaction (IAR) and will be identified by patients recording is the event an Infusion-Associated Reaction (IAR)? as “Yes”. ADR will be summarized by SOC/ PT and presented as listing.

## 17.2 Deaths

Deaths during the study presented in a data listing for ITT population.

## 17.3 Laboratory Evaluations

Results from the central laboratory and local laboratory will be included in the reporting of this study for Hematology, Blood Chemistry, Coagulation, Urinalysis, and Renal Functions (blood urea nitrogen, eGFR, urine albumin-creatinine ratio, electrolytes(Sodium, Potassium, Bicarbonate, Chlorine, Magnesium, Calcium), and phosphate from blood and Urine Samples).

Quantitative laboratory measurements reported as “< X”, i.e. below the lower limit of quantification (BLQ), or “> X”, i.e. above the upper limit of quantification (ULQ), will be converted to X for the purpose of quantitative summaries, but will be presented as recorded, i.e. as “< X” or “> X” in the listings.

Laboratory tests which will be included in summaries are provided below:

- **Hematology:** Complete hemogram, %Reticulocytes, Platelet count, White blood cell count with differential, Red blood cell count, Neutrophils, Hemoglobin, Lymphocytes, Hematocrit, Monocytes, Red blood cell indices, Eosinophils, Mean corpuscular volume, Basophils, Mean corpuscular hemoglobin, Mean cell hemoglobin concentration.
- **Chemistry:**, Creatinine, Total cholesterol, Cholesterol LDL, Cholesterol HDL, Triglycerides, Glycemia, Total bilirubin, Alkaline phosphatase, Direct bilirubin, Total proteins, Aspartate aminotransferase, Albumin, Alanine aminotransferase, Gamma glutamyl transferase
- **Urinalysis:** First morning urine(visual exam, dipstick test and microscopic exam (color, clarity, pH, specific gravity, glucose, blood, ketones, protein, urobilinogen, bilirubin, leukocyte esterase, nitrite, blood, white blood cells, red blood cells, epithelial cells, crystals, and casts).

The following summaries will be provided for laboratory data:

- Actual and change from baseline by visit (for quantitative measurements)
- The count and percentage of patients for Urinalysis (Discrete measurements)
- Incidence of abnormal values according to Clinical significance criteria

---

Document: \\eedc-vnasc01\Biosdata\Biosidus\Agalsidase Beta\YZAA1358\Biostatistics\Documentation\SAP

Author: [name]

Version Number: V1.0

Version Date: 08May2025

Template No.: CS\_TP\_BS016 Revision 7

Reference: CS\_WI\_BS005

Effective Date: 01Nov2021

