### Medical Conditions

1. Chronic kidney disease in stage 3b, 4, or 5.
2. History of dialysis, kidney transplant or participants who are on the waiting list for a kidney transplant.
3. Proteinuria  $\geq 1$  g/day at screening.
4. Participants who have suffered a clinical cardiovascular event (such as but not limited to myocardial infarction, transient ischemic attack) within 6 months prior to Screening visit.
5. Participants who have clinically significant unstable cardiac disease (such as but not limited to uncontrolled symptomatic arrhythmia, unstable angina, congestive heart failure New York Heart Association class III or IV).
6. Participants who have suffered a clinical cerebrovascular event (such as but not limited to stroke, transient ischemic attack) within 6 months prior to Screening visit.
7. History of anaphylaxis or other type I hypersensitivity reactions to agalsidase beta.

8. History of acute kidney injury in the 12 months prior to Screening visit (such as but not limited to acute interstitial nephritis, acute renal failure of glomerular origin or caused by vasculitis).
9. Presence of any medical, emotional, behavioral, or psychological condition that, according to the Investigator, would interfere with the participant's compliance with the requirements of the study.

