## 10.5 Appendix 5: AEs and SAEs: Definitions and Procedures for Recording, Evaluating, Follow-up, and Reporting for Study Intervention

### 10.5.1 Definition of Adverse Event

AE Definition

 
• An AE is any untoward medical occurrence in a clinical study participant administered a medicinal product and which does not necessarily have a causal relationship with that product.
 
• NOTE: An AE can therefore be any unfavorable and unintended sign (including an abnormal laboratory finding, for example), symptom, or disease (new or exacerbated) temporally associated with the use of study intervention/treatment, whether or not considered related to the study intervention/treatment.
 

Events Meeting the AE Definition

 
• Any abnormal laboratory test results (hematology, clinical chemistry, or urinalysis) or other safety assessments (eg, ECG, echocardiogram, vital signs measurements), including those that worsen from baseline, considered clinically significant in the medical and scientific judgment of the Investigator (ie, not related to progression of underlying disease).
 
• Exacerbation of a chronic or intermittent pre-existing condition including either an increase in frequency and/or intensity of the condition.
 
• New condition detected or diagnosed after study intervention administration even though it may have been present before the start of the study.
 
• Signs, symptoms, or the clinical sequelae of a suspected intervention-intervention interaction.
 
• Lack of efficacy or failure of expected pharmacological action per se will not be reported as an AE or SAE. Such instances will be captured in the efficacy assessments. However, the signs, symptoms, and/or clinical sequelae resulting from lack of efficacy will be reported as AE or SAE if they fulfill the definition of an AE or SAE.
 

Events NOT Meeting the AE Definition

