## 6.2 Baseline

Unless otherwise specified, baseline is defined as the last observed value of the parameter of interest prior to the first intake of AGA BETA BS (this includes unscheduled visits). In the case where the date of last non-missing measurement and the reference start date coincide, then collection time, where available, will be compared with the first dose time to determine whether the measurement is pre-baseline or post-baseline. If time is not available or if assessment time coincides with reference start time, the measurement will be considered pre-baseline, but adverse events (AEs), medications commencing on the reference start date will be considered post-baseline.

Any assessment collected prior to intake of AGA BETA BS will be part of Lead-in period.

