### 17.3.2 Laboratory Reference Ranges and Markedly Abnormal Criteria

Quantitative laboratory measurements will be compared with the relevant laboratory reference ranges in SI units and categorized as:

- Low: Below the lower limit of the laboratory reference range.
- Normal: Within the laboratory reference range (upper and lower limit included).
- High: Above the upper limit of the laboratory reference range.

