## 17.4 ECG Evaluations

Results from the central ECG (Electrocardiogram) Reading Centre will be included in the reporting of this study. Results for ECG will be presented under SAF.

The following ECG parameters will be reported for this study:

- Heart Rate (beats/min)
- PR Interval (msec)
- QRS Interval (msec)
- QT Interval (msec)
- QTcF Interval (msec)
- QTcB Interval (msec)
- Overall ECG Evaluation (Investigator's judgment):

The following summaries will be provided for ECG data:

- Actual and change from baseline by visit (for quantitative measurements)
- The count and percentage of patients for overall ECG interpretation will be provided as follows
- Normal
- Abnormal, Not Clinically Significant (NCS)
- Abnormal, Clinically Significant (CS)

A patient wise listing of 12 Lead ECG findings will be provided.

---

Document: \\needc-vnasc01\Biosdata\Biosidus\Agalsidase Beta\YZAA1358\Biostatistics\Documentation\SAP

Author: [name]

Version Number: V1.0

Version Date: 08May2025

Template No.: CS\_TP\_BS016 Revision 7

Reference: CS\_WI\_BS005

Effective Date: 01Nov2021

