## 17.8 Echocardiogram

Results from the Echocardiogram will be included in the reporting of this study. Results for Echocardiogram will be presented under SAF.

The following Echocardiogram parameters will be reported for this study:

- Thickness of the Left Ventricular Wall
- Left Ventricular Mass index
- Left ventricular ejection fraction
- Overall Evaluation

The following summaries will be provided for Echocardiogram data:

- Actual and change from baseline by visit (for quantitative measurements)
- The count and percentage of patients for overall Echocardiogram interpretation will be provided as follows

Normal

Abnormal, Not Clinically Significant (NCS)

Abnormal, Clinically Significant (CS)

A patient wise listing of Echocardiogram findings will be provided.

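### In the readable SAP text, the categorical laboratory, urinalysis, ECG and echocardiogram summaries are not referenced to baseline class, so they cannot separate new abnormalities from carried-over ones.

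*SAP*

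**What the plan says.** **Laboratory (SAP 17.3, 17.3.2).** Three summaries are listed. The first, "Actual and change from baseline by visit (for quantitative measurements"), refers to baseline but covers numeric values only. The second is a count and percentage for discrete urinalysis. The third is "Incidence of abnormal values according to Clinical significance criteria", with no denominator, no rule for a new or worsened value and no definition of the criteria. SAP 17.3.2 adds classes: "Quantitative laboratory measurements will be compared with the relevant laboratory reference ranges in SI units and categorized as" low, normal or high. No output crosses these with the class at baseline.

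**ECG (SAP 17.4).** "The count and percentage of patients for overall ECG interpretation will be provided as follows": normal, abnormal not clinically significant, abnormal clinically significant. Change from baseline is again confined to numeric parameters.

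**Echocardiogram (SAP 17.8).** The same three classes and the same structure: "The count and percentage of patients for overall Echocardiogram interpretation will be provided as follows".

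**Baseline (SAP 6.2).** "baseline is defined as the last observed value of the parameter of interest prior to the first intake of AGA BETA BS". Baseline therefore reflects treatment with Fabrazyme, and it need not fall on Day 1.

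**Protocol 9.2.5.** It commits to baseline-change analyses of the cardiac tests at weeks 26 and 54. For laboratory data it allows change from baseline, counts and percentages as applicable.

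**The concern.** The trial has one group and is controlled by each participant's own baseline. A safety table that leaves out baseline status cannot show what changed after the switch.

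Abnormal findings at entry are to be expected. Fabry disease affects the kidneys and heart. The renal exclusion is "Chronic kidney disease in stage 3b, 4, or 5", and inclusion criterion 12 admits an eGFR down to 45 mL/min/1.73 m². Proteinuria below 1 g/day is allowed, and cardiac disease excludes a participant only if it is clinically significant and unstable.

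The renal and cardiac safety endpoints are meant to show whether organ function holds up on AGA BETA BS. A class count without baseline can mislead in two ways. A stable finding already present on Fabrazyme appears in the AGA BETA BS column with nothing to mark it as old. A flat count may hide new abnormalities offset by others that resolved. The SAP has a treatment-emergence rule for adverse events (17.1, Appendix 2) but states none for these data.

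**Working it through.** The plan gives no figure here to reproduce. The check is a reading of the text, followed by a count.

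**Step 1: text.** The laboratory, ECG and echocardiogram sections were read for a shift table, a new-or-worsened rule, or a denominator limited to participants normal at baseline. None is described. Laboratory-specific derivations (SAP 17.3.1) are marked not applicable. The incidence line does not say whether it counts per visit or cumulatively, and the ECG and echocardiogram class lines name no visit.

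**Step 2: inputs for an illustration.**
- N = 20, the planned maximum (SAP 3.1).
- B, number abnormal at baseline: assumed 6, 10 or 14 (30% to 70%). Not in the documents.
- R resolved and W new: assumed equal, at 0, 2 or 4. Not in the documents.

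**Step 3: formulas.**
- Count abnormal at a later visit = B − R + W.
- Proportion newly abnormal among those at risk = W / (N − B).

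**Step 4: results.**

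| B | R = W | Baseline count | Later count | Newly abnormal among those normal at baseline |
|---|---|---|---|---|
| 6 | 0 | 6/20 = 30% | 6/20 = 30% | 0/14 = 0% |
| 6 | 2 | 6/20 = 30% | 6/20 = 30% | 2/14 = 14.3% |
| 6 | 4 | 6/20 = 30% | 6/20 = 30% | 4/14 = 28.6% |
| 10 | 0 | 10/20 = 50% | 10/20 = 50% | 0/10 = 0% |
| 10 | 2 | 10/20 = 50% | 10/20 = 50% | 2/10 = 20.0% |
| 10 | 4 | 10/20 = 50% | 10/20 = 50% | 4/10 = 40.0% |
| 14 | 0 | 14/20 = 70% | 14/20 = 70% | 0/6 = 0% |
| 14 | 2 | 14/20 = 70% | 14/20 = 70% | 2/6 = 33.3% |
| 14 | 4 | 14/20 = 70% | 14/20 = 70% | 4/6 = 66.7% |

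For a given B, the three rows look the same in a by-visit count. With R = W = 0, every abnormality counted on AGA BETA BS is carried over.

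**Step 5: cumulative reading.** A count of participants abnormal at any visit after baseline does not hide new cases, but it mixes them with old ones. With B = 6 and R = W = 2 it lies between 6 − 2 + 2 = 6 and 6 + 2 = 8 of 20 (30% to 40%), depending on when the two findings resolve. Only 2 of those participants are new cases.

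Masking therefore belongs to the by-visit reading and mixing to the cumulative one. A single table cannot show both.

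**The case against.** The strongest reply is that much of the question is answered elsewhere.

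- **Numeric parameters.** eGFR, albumin-creatinine ratio, ECG intervals, wall thickness, left ventricular mass index and ejection fraction all have change from baseline, with quartiles and extremes (SAP 6). This stands. It confines the gap to categorical results.
- **Laboratory clinical significance.** Protocol 8.3.5 treats disease-related laboratory abnormalities as not clinically significant unless the investigator finds them worse than the participant's condition would explain. If the undefined criteria in SAP 17.3 mean that judgment, many stable Fabry findings would leave the count. A reader might infer that the laboratory line charges stable Fabry abnormalities to AGA BETA BS; the documents do not support that as stated. The rule speaks of laboratory findings, so it does not settle the ECG and echocardiogram classes.
- **Adverse events.** Abnormal safety assessments qualify as adverse events, "including those that worsen from baseline, considered clinically significant in the medical and scientific judgment of the Investigator", and those events have an emergence rule. This route is partial: the same sentence excludes progression of the underlying disease, and protocol 10.5.1 excludes expected progression unless more severe than expected.
- **Listings.** With about 20 participants, a change of class can be read from the by-patient ECG and echocardiogram listings. That is true, but a listing is not a planned summary.
- **Table shells.** SAP 8 leaves format and content to templates that are not in the public text. A shift table there cannot be ruled out.
- **Consequence.** Safety is descriptive, and no decision rule rests on these counts.

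**Conclusion.** The point holds for the categorical summaries in the readable SAP text: overall ECG and echocardiogram readings, discrete urinalysis, laboratory reference-range classes and the incidence of abnormal laboratory values. It is clearest for ECG and echocardiogram, because protocol 9.2.5 promises change from baseline for those tests and the SAP delivers it only for their numeric parameters.

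The size is illustrative. With 2 new and 2 resolved findings among 20 participants, a by-visit count stays flat while 14.3% to 33.3% of those normal at baseline become abnormal; with 4 and 4 the range is 28.6% to 66.7%. These rest on the assumed 30% to 70% abnormal at baseline and on equal numbers new and resolved. They show what the tables could fail to reveal, not what is likely.

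Two stronger readings are not supported. One is that the SAP's incidence is really prevalence: the term is undefined, and that is the defect. The other is that deterioration would go unseen: numeric change from baseline, listings and adverse-event reporting each cover part of it. If class counts are also shown at baseline, prevalence before and after can be compared, but individual shifts still cannot.

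**What to change.** In SAP 17.3, 17.4 and 17.8, on the Safety Population:

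1. Add shift tables from the SAP 6.2 baseline class to each scheduled visit and to the worst post-baseline class, for the overall ECG and echocardiogram readings. Do the same for laboratory reference-range classes and discrete urinalysis.
2. Define laboratory incidence as a new or worsened class after the first AGA BETA BS infusion, with participants at risk at baseline as the denominator.
3. State what the clinical-significance criteria are and who applies them.
4. Use the SAP 6.2 baseline as the anchor, not the Day 1 value, since the last value before the first infusion may be earlier.

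If the table shells already contain such shifts, it is enough to name them in the SAP text.

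Cost: SAP wording and a few more descriptive tables from data already collected. With about 20 participants many cells will be small, so the tables should be read as counts.

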### 17.3.1 Laboratory Specific Derivations

Not Applicable

### 17.3.2 Laboratory Reference Ranges and Markedly Abnormal Criteria

Quantitative laboratory measurements will be compared with the relevant laboratory reference ranges in SI units and categorized as:

- Low: Below the lower limit of the laboratory reference range.
- Normal: Within the laboratory reference range (upper and lower limit included).
- High: Above the upper limit of the laboratory reference range.

## 17.4 ECG Evaluations

Results from the central ECG (Electrocardiogram) Reading Centre will be included in the reporting of this study. Results for ECG will be presented under SAF.

The following ECG parameters will be reported for this study:

- Heart Rate (beats/min)
- PR Interval (msec)
- QRS Interval (msec)
- QT Interval (msec)
- QTcF Interval (msec)
- QTcB Interval (msec)
- Overall ECG Evaluation (Investigator's judgment):

The following summaries will be provided for ECG data:

- Actual and change from baseline by visit (for quantitative measurements)
- The count and percentage of patients for overall ECG interpretation will be provided as follows
- Normal
- Abnormal, Not Clinically Significant (NCS)
- Abnormal, Clinically Significant (CS)

A patient wise listing of 12 Lead ECG findings will be provided.

---

Document: \\needc-vnasc01\Biosdata\Biosidus\Agalsidase Beta\YZAA1358\Biostatistics\Documentation\SAP

Author: [name]

Version Number: V1.0

Version Date: 08May2025

Template No.: CS\_TP\_BS016 Revision 7

Reference: CS\_WI\_BS005

Effective Date: 01Nov2021

## 17.5 Vital Signs

The following Vital Signs measurements will be reported for this study:

- Systolic Blood Pressure (mmHg)
- Diastolic Blood Pressure (mmHg)
- Heart (Bpm)
- Respiratory Rate (resp/min)
- Body Temperature (axillary) (°C)
- Weight (Kg)
- BMI (kg/m^2)

The following summaries will be provided for vital signs data:

- Actual and change in vital signs by visit.
- Listing of patients' vital signs.

For all measurements including before and hourly during the infusions, blood pressure, heart rate, and respiratory rate will be assessed in a sitting position after 5 minutes rest for the patient in a quiet setting without distractions (eg, television, cell phones), with a device previously calibrated or as determined by the manufacturer.

Three readings of blood pressure and heart rate will be taken. The first reading should be rejected. The second and third readings should be averaged to give the measurement to be recorded.

Data from both Vital signs and Vital Signs Dosing page of CRF will be presented for SAF population for average reading for applicable parameters.

## 17.6 Immunogenicity Assessments

Results for Immunogenicity analysis will be presented under SAF population. The following analyses will be performed: Number and frequency of patients with ADA Neutralization Results to AGA BETA BS sampling results by visit

o Negative

o Positive

o Not Done

Descriptive statistics for percentage neutralization will be provided for all available parameters at protocol specified visits using Number of patients available at each assessment visit, Arithmetic Mean, Median, Minimum Maximum, quartiles and Geometric Mean. Summaries for both Actual and change from baseline will be presented. For geometric mean, the mean and the 95% CIs will be calculated on log transformed data, with subsequent antilog transformations applied.

Document: \\needc-vnasc01\Biosdata\Biosidus\Agalsidase Beta\YZAA1358\Biostatistics\Documentation\SAP

Author: [name]

Version Number: V1.0

Version Date: 08May2025

Template No.: CS\_TP\_BS016 Revision 7

Reference: CS\_WI\_BS005

Effective Date: 01Nov2021

## 17.7 Physical Examination

A patient wise listing of physical examination findings as collected in eCRF will be provided on SAF.

## 17.8 Echocardiogram

Results from the Echocardiogram will be included in the reporting of this study. Results for Echocardiogram will be presented under SAF.

The following Echocardiogram parameters will be reported for this study:

- Thickness of the Left Ventricular Wall
- Left Ventricular Mass index
- Left ventricular ejection fraction
- Overall Evaluation

The following summaries will be provided for Echocardiogram data:

- Actual and change from baseline by visit (for quantitative measurements)
- The count and percentage of patients for overall Echocardiogram interpretation will be provided as follows

Normal

Abnormal, Not Clinically Significant (NCS)

Abnormal, Clinically Significant (CS)

A patient wise listing of Echocardiogram findings will be provided.

